on faces from the Pictures of Facial Affect stimuli set [PFA; 98]. Words are centered horizontally within the frame and vertically at vertical midpoint of the nose. Words are presented at 25% opacity (Fig. 2). Ss are instructed to respond to the *word* presented as quickly and accurately as possible. Ss respond to the word by pressing a corresponding response key. Three responses are possible: HAPPY, SAD, and ANGRY. Ss respond with their dominant hand on labeled keyboard keys. The overlaid words were taken from a list of eight emotion adjectives prototypical of the three emotional response categories [99; see Appendix]. Trials will consist of congruent (word and face have matching emotions), incongruent (word and face expressions do not match), and neutral (neutral face) conditions. Four emotions (HAPPY, SAD, ANGRY, NEUTRAL) from four actors in the PFA set will be used (2 men; 2 women). The combination

Fig 2. Example of a congruent trial w/congruent word & facial emotion

of these 16 facial stimuli and 24 adjectives creates a pool of 384 unique stimuli. From this pool, Ss will view 192 congruent stimuli, 96 neutral stimuli, and 96 incongruent stimuli (384 total trials). The higher proportion of congruent trials are used because Stroop effects (>RT on incongruent trials) are known to be sensitive to habituation. No stimuli will be repeated more than once. Stimuli will remain on the screen until Ss respond or 5 secs have elapsed (resulting in an omission). A colored (red/green for correct/incorrect) border provides accuracy feedback. Schwiezer's timing of 500 msec for feedback and ITI will be tested and adjusted, as needed, during task development. Dependent variables will include RT, ACC in each emotion/congruency condition, and efficiency (ACC/RT), with particular interest in the incongruent conditions. *Time: ~15 min.*

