Directed Attend/Ignore Task Ss will also train on a task developed by Gazzaley et al. [13] to examine top-down control processes directing selective attention and modified from our previous work [100]. Ss are directed to either "Remember faces but ignore scenes" or "Remember scenes but ignore faces". [See Fig. 4]. Following a delay, a probe stimulus is provided (either face or scene, depending on instructional set) and Ss indicate via button

Fig 4. Modified from Gazzaley et al., 2008. Lines below the cue stimuli reflect task relevance for illustration and are not present during task administration.

press whether the probe stimulus matched the presentation stimuli. Each training session will include 4 blocks (2 per instructional set) of 20 trials. The duration of stimuli presentation and delay intervals used at training initiation are depicted in Fig 4. Task difficulty will change dynamically with Ss' performance with improved accuracy resulting in extended delay time and shortened stimulus presentation.. *Training Time:* \sim 25 *min/day*

Post-Training Assessment/Retesting. Within 1-5 days following training completion (dictated by discharge dates), Ss will be re-administered the BDI-II, AI, the emotional Stroop, and the cognitive efficiency battery. Time: ~ 1 hr. Reimbursement: \$25.

Follow-up. Follow-up interviews are conducted approximately 30, 60, and 90 days following treatment discharge (or post-training assessment, for outpatient participants). Interviews use the Project MATCH's modification of the timeline follow-back [TLFB; 102, 103] for assessing quantity and frequency of daily substance use (alcohol, nicotine, other drugs) over the previous month. Ss also complete the "Your friends and family" items from Moos' Health and Daily Living Scales [104]. The Profile of Mood States (POMS) 2-A Short [105] and Mini Alcohol Craving Experience questionnaire [107] will also be administered. Ss receive \$20 for each completed follow-up interview. Estimates suggest that ~ 60% of the sample will complete all interviews. *Time: ~30 min.* [See Appendix for listing]

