Data Analysis Strategy. General considerations: Statistical analyses will apply SAS Version 9.4 (SAS Institute). Data will be examined for completeness, outliers, and distributional fit with transformations employed, as appropriate. Descriptive statistics, graphical methods and correlational matrices will be used to characterize the data. To examine outcomes over time generalized linear mixed models (GLMM) and linear contrasts will be used. Dependent variables are noted in task descriptions. Aims 1-3 are addressed in both transfer and training analyses, *Feasibility*: The design should minimize dropout, however we will evaluate dropout rates and the number of trainings completed prior to dropout as a function of sex, training condition, and the interaction. For selected analyses, missing data techniques will be employed; pattern-mixture models based on point of loss and sensitivity analysis will aid in interpretation. Transfer effects: GLMM analyses will be employed to examine effects of training condition, sex, and their interaction on transfer task performance. Dependent variables include RT, ACC, and efficiency (ACC/RT) for each Stroop condition (congruent, incongruent, neutral) and the cognitive battery. Training Effects: Linear contrasts will be utilized to compare performance on the training tasks across training session, group, and sex. We will explore whether the two training tasks are differentially related to transfer of gains. Secondary aim: Exploratory methods will be applied to a) examine associations between/among measures of functional adaptation, mood/affect, transfer gains and post-treatment substance use, and b) explore potential subgroups/subtypes that vary in response to training and/or post-treatment outcomes. Training session ratings of acceptability and perceived improvement will be compiled to provide proxy indicators of engagement to inform training session development. Power: Schweizer et al. [60], report large transfer effects (Cohen's f's, .82-1.10) but do not address sex differences. Given the developmental nature of the investigation and the intent to identify preliminary data regarding sex differences meriting further study, we will consider sex main effects at $\alpha = .10$. With an estimated moderate effect size (Cohen's f=.25) and a correlation between measures of rho=.5, our power to detect sex effects is .78. Our power to detect transfer effects relative to controls is 1.0 with power =.98 to detect more modest between-group training effects (Cohen's f ~.40; α =.05). For the critical interaction of sex and training condition, and estimating a moderate effect, our power is .96 (α = .05, rho = .5). This estimate fails to account for Ss dropout. Absent guiding estimates, we conducted an analysis with a dropout of 10 Ss/ condition and maintained power =.80.

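### Can the emotional Stroop's 192 congruent, 96 neutral and 96 incongruent trials come from its pool of 384 face-word pairs?

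*Combined protocol and SAP*

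**What the plan says.** Section 6 (Research Plan), under Emotional Stroop, defines the faces as follows: "Four emotions (HAPPY, SAD, ANGRY, NEUTRAL) from four actors in the PFA set will be used (2 men; 2 women". On the words it says: "The overlaid words were taken from a list of eight emotion adjectives prototypical of the three emotional response categories". It then states that the combination "of these 16 facial stimuli and 24 adjectives creates a pool of 384 unique stimuli", and gives the counts by condition: "From this pool, Ss will view 192 congruent stimuli, 96 neutral stimuli, and 96 incongruent stimuli (384 total trials". A trial is congruent when word and face carry the same emotion, incongruent when they differ, and neutral when the face is neutral. The surplus of congruent trials is deliberate: the protocol argues that interference on incongruent trials wears off with exposure. On repetition it says: "No stimuli will be repeated more than once".

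The outcomes are set condition by condition. The task description says: "Dependent variables will include RT, ACC in each emotion/congruency condition, and efficiency (ACC/RT), with particular interest in the incongruent conditions". The Data Analysis Strategy, under transfer effects, says: "Dependent variables include RT, ACC, and efficiency (ACC/RT) for each Stroop condition (congruent, incongruent, neutral) and the cognitive battery". At the post-training visit, "Ss will be re-administered the BDI-II, AI, the emotional Stroop, and the cognitive efficiency battery".

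**The concern.** The pool has 384 members and the task has 384 trials, so the natural first reading is that each pair is shown once. That reading fails. Running through the pool once gives 96 congruent, 96 neutral and 192 incongruent trials. Incongruent trials would then be the majority, which reverses the stated 2:1:1 ratio and defeats the reason given for it. The same noun is used for pool members and for presentations, and the repetition rule can be misread as allowing each item only one appearance. Under that misreading, 192 congruent trials are impossible.

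The emotional Stroop is one of the two tasks that supply the primary dependent variables. If its counts could not be met, or if two people could build materially different tasks from the paragraph, the measurement of the main outcome would be in doubt. Repetition that fell only on congruent trials would also affect any congruent-versus-incongruent difference score.

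**Working it through.** **Inputs** (all from the Emotional Stroop description): 4 actors; 4 expressions, of which 3 are emotional and 1 is neutral; 24 adjectives over 3 response categories; at most one repeat per item; about 15 minutes; a 5-second response limit.

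**The plan's own totals.**
- Faces: 4 × 4 = 16.
- Pool: 16 × 24 = 384.
- Trials: 192 + 96 + 96 = 384.

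All three reproduce. The eight adjectives must mean eight per category (3 × 8 = 24); eight in all would give 16 × 8 = 128.

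**Pool by condition.**
- Neutral: 4 neutral faces × 24 words = 96.
- Congruent: each word matches one expression, shown by 4 actors: 24 × 1 × 4 = 96.
- Incongruent: each word mismatches two expressions: 24 × 2 × 4 = 192.
- Sum: 96 + 96 + 192 = 384.

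The split depends only on the total of 24 words. Enumerating unequal categories (10/7/7, 12/6/6 and 20/2/2) gives the same 96/96/192.

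**Can the stated counts be met?**

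| Condition | Pool | Stated trials | Trials per item | One showing each | Up to two showings |
|---|---|---|---|---|---|
| Congruent | 96 | 192 | 2.0 | no | yes, exactly |
| Neutral | 96 | 96 | 1.0 | yes | yes |
| Incongruent | 192 | 96 | 0.5 | yes | yes |

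One repeat means two showings, and 2 × 96 = 192. The congruent list is therefore fully fixed: all 96 pairs, each shown twice.

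**What stays open.** With *d* distinct items filling 96 trials at one or two showings each, *d* runs from 48 to 96, and the share of second showings is (96 − *d*)/96. That is 50% at *d* = 48, 25% at *d* = 72 and 0% at *d* = 96. It applies separately to neutral and to incongruent trials. For congruent trials the share is fixed at 96/192 = 50%. Over the whole task, distinct items number between 96 + 48 + 48 = 192 and 96 + 96 + 96 = 288, so between 384 − 288 = 96 and 384 − 192 = 192 trials are repeats.

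**Check against the stated duration.** 15 × 60 = 900 s. Over 384 trials that is 900/384 = 2.3 s per trial. If each item could appear only once, the 2:1:1 ratio would cap the task at 96 + 48 + 48 = 192 trials, or 900/192 = 4.7 s each, close to the 5-second limit. The duration fits 384 presentations better.

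**Effect on the planned comparisons.** Let *r* be the share of second showings in a condition and δ the average speed gain on a second showing. That condition's mean RT is then the first-showing mean minus *r*δ. With one task, *r* is the same in every arm and at both visits, so the term *r*δ is common to the arms and drops out of the difference in pre-post change, unless training itself alters δ. The same reasoning covers accuracy and efficiency: every participant takes the same test.

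**The case for a change.** The best case for a change is that this is a primary measure, that the incongruent condition is singled out for attention, and that it is the condition whose item selection is least described. The number of trials for each face-word emotion pairing depends on that selection. For the training tasks the protocol does state a balance rule (each face model appears equally often across affect categories); for the emotional Stroop it states none. A sentence and an item list would cost very little.

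Part of this stands. The supplied text does not say which 96 of the 192 incongruent pairs are used, or whether neutral and incongruent items repeat, and the loose use of one noun for items and presentations invites misreading.

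The rest is weaker. A one-repeat limit presupposes repeats, and here it settles the congruent list exactly. The Appendix cited for the word list is not in the supplied text and may hold more, although the pointer is attached to the words and not to the face-word pairs. A congruent-versus-incongruent difference score is where unequal repetition would matter, but the plan does not name one as a dependent variable.

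Nor is there an obvious better build to require. Showing 96 congruent, 48 neutral and 48 incongruent pairs twice each keeps every stated count and equalises repetition. It also halves the distinct incongruent pairs from 96 to 48 and repeats every one of them, in a task whose design rests on the worry that the interference effect habituates. Showing 96 different incongruent pairs once is at least as defensible.

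**Conclusion.** The concern does not call for a change. It is right that 192/96/96 cannot be 384 distinct pairs, since the pool holds 96/96/192. But the plan presents the counts as trials and allows one repeat, and on that basis they can be met exactly. What remains is loose wording and an item list that whoever programs the task has to settle. The open range is 0% to 50% second showings among neutral and incongruent trials. No effect in milliseconds can be derived from the documents, and no planned comparison is shown to be biased.

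This rests on two assumptions: the repetition rule is read literally, as up to two showings; and one item list serves all arms and both visits, which is the ordinary meaning of re-administering the task. The 384 trials, the planned analyses and the stated sample size, alpha and power are all unaffected.

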Summary. There is renewed interest in determining whether cognitive retraining directed to enhancing performance on underlying component processes may improve the effectiveness of treatment for SUDs. Current studies offer promise and suggest directions for additional research. This project is designed to address two areas of clinical and scientific relevance; the systematic inclusion of women and the extension of training paradigms to consider transfer of gains to tasks engaging emotion processing. Additionally, given the limited data on longer-term effects, we will extend the follow-up to cover the first 90 days following discharge, i.e., through a known period of heightened vulnerability [79].

Overall Summary. Neurobehavioral deficits are common in treatment-seeking persons with AUDs. Cognitive training directed to commonly compromised processes shows promise and merits further research. As a pilot project, the scope of work is necessarily limited. In this application, we seek to extend current work by examining sex differences in response to cognitive training in attention/working memory and by investigating whether training engaging emotion processes differentially affects outcomes, and if the sexes differ in their response to this training. We will also examine relationships among demographic variables, comorbid substance use, performance gains, and post-treatment outcomes (i.e., over a 3 month period), thereby providing direction for consideration of individual differences in training outcomes. Together these data will inform questions of feasibility, identify potential subgroups (beyond sex) varying in response, and guide the development of a more comprehensive R01 application assessing cognitive training among treatment-seekers with AUDs.

5. Aims (H=hypothesis, E=empirical question)

Aim 1: Investigate potential sex differences in response to cognitive training. In the absence of a consistent literature, we ask: **E1:** Will men and women show differential transfer of gains in post-intervention testing? **E2:** Will transfer of gains for men vs. women differ on the basis of transfer task demands? **E3**: Will they differ in the degree to which they demonstrate improvement across training? **E4**: Will the relationship between baseline performance, training gains, relapse and/or post-treatment adaptation differ for women and men?

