- 103. Miller WR. What is a relapse? Fifty ways to leave the wagon. Addiction. 1996;91 Suppl:S15-27. PMID: 8997778.

7. Possible Discomforts and Risks

Selection criteriaDetoxified alcohol dependent Ss (N=90; 45 women) will be recruited from inpatient, residential and intensive outpatient alcohol/drug treatment facilities across north central Florida. Ss will be between 25-65 with a minimum of 10 years of education. Ss will have completed medical detoxification (if it was required) and be abstinent from psychoactive drugs used to manage withdrawal symptoms. Only Ss reporting chronicity of alcohol problems \geq 5 yrs will be recruited. This threshold has not unduly compromised recruitment in previous work with this population. Given the reported rates of cigarette smoking in our treatment populations (~88%), current and past smoking history will be queried and data will be used in descriptive and correlational analyses.

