Protection Against Risk: To protect privacy, individuals complete the screening packet in an area separate from clinical activities with the aid of trained research assistants. The SCID-5, baseline assessment, computerized training, and post-intervention assessment are administered in designated rooms at the treatment facilities. To protect against potential breaches of confidentiality, data are coded by a number unrelated to the subject and cannot be directly connected to individual Ss. Data are reported in aggregate form wherein no individuals can be identified, and stored on the Department of Psychiatry's encrypted and password-protected server. Additionally, Ss are protected by a Certificate of Confidentiality.

Ss may withdraw at any point in the screening, testing, or training sessions without impact on clinical care. If Ss discontinue during the conduct of the active study, they receive prorated compensation. Follow-up interviews are reimbursed after each completed interview.

8. Possible Benefits

Individuals in the training groups may experience some improvements in cognitive performance.

9. Conflict of Interest

There is no conflict of interest beyond the professional benefit from academic publication or presentation of the results.

DATA AND SAFETY MONITORING PLAN (approved by NIAAA)

The demonstration/pilot project involves the recruitment of otherwise healthy men and women seeking treatment for a substance use disorder. Individuals with medical or comorbid psychiatric disorders that would confound interpretation of neurocognitive function are excluded from study. Depending on the phase of the project, qualifying and consenting participants are assigned to the control group, or randomly assigned to one of the two active computerized training groups (affective vs. neutral), with the constraint that every attempt is made to recruit equal numbers of men and women across the three groups. Cognitive capacity is assessed prior to the intervention and tracked across the intervention (multiple sessions across multiple weeks). After the intervention, all participants are contacted by phone and provide feedback regarding post-treatment drinking and psychosocial adaptation at three time-points (30, 60, and 90 days post-treatment). The intervention does not involve the administration of alcohol or any other drug or pharmacological agent.

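### The follow-up interviews use a one-month recall with no stated catch-up rule, so a missed day-30 or day-60 call, or a late call, leaves days of substance use unrecorded

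*Combined protocol and SAP*

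**What the plan says.** All references are to the combined protocol and SAP.

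- **Section 6, Follow-up (schedule).** "Follow-up interviews are conducted approximately 30, 60, and 90 days following treatment discharge". For outpatients the anchor is the post-training assessment instead. No tolerance around these days is given.
- **Section 6, Follow-up (recall).** The timeline follow-back covers "quantity and frequency of daily substance use (alcohol, nicotine, other drugs) over the previous month".
- **Section 6, Follow-up (completion).** "Estimates suggest that ~ 60% of the sample will complete all interviews".
- **Section 4, Summary on cognitive training.** The stated purpose is that "we will extend the follow-up to cover the first 90 days following discharge", described there as a time of raised vulnerability.
- **Section 6, Data Analysis Strategy.** "For selected analyses, missing data techniques will be employed; pattern-mixture models based on point of loss and sensitivity analysis will aid in interpretation". The substance-use data enter the secondary aim, which will "examine associations between/among measures of functional adaptation, mood/affect, transfer gains and post-treatment substance use".
- **Data and Safety Monitoring Plan.** It repeats the three time-points and adds no rule for a missed or late call.

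The Follow-up paragraph ends by pointing to an Appendix, which is not in the supplied text.

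**The concern.** When every call is on time, a one-month recall and a recall back to the last interview cover the same days. They differ once a call is missed or late. The plan expects about 40% of participants to miss at least one call, and it describes the timing as approximate, so this will not be rare.

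Take a participant who misses day 30 and is reached on days 60 and 90. Followed as written, the interviews record days 31 to 90 and nothing before. If drinking is reported in that span, it cannot be shown to be the first drinking since discharge. If none is reported, abstinence over the 90 days is still unproven.

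E4 asks whether the links between baseline performance, training gains, relapse and adaptation differ by sex, and the secondary aim relates transfer gains to later use. Both draw on this record. The primary outcomes, the pre-post Stroop differences, do not. The planned missing-data techniques can model the gap but cannot recover days that the participant was available to report.

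**Working it through.** The plan gives no figure for this point other than the 60% estimate, so there is nothing of its own to reproduce. The check counts the days covered under each recall rule.

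**Inputs from the documents.** Calls at days 30, 60 and 90; recall of one month; about 60% completing all three; N = 90 (section 7, selection criteria: "Detoxified alcohol dependent Ss (N=90; 45 women) will be recruited"); intended coverage of days 1 to 90.

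**Assumptions.** A month is 30 days; all 90 participants enter follow-up; 10 days is used as an example of a late call.

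**Step 1: days 1-90 covered per participant**

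| Pattern of calls | One-month recall | Recall to last completed interview |
|---|---|---|
| All on time | 90 | 90 |
| Day 30 missed | 60 | 90 |
| Day 60 missed | 60 | 90 |
| Days 30 and 60 missed, day 90 reached | 30 | 90 |
| Day 90 missed | 60 | 60 |
| One call 10 days late | 80 | 90 |
| All three 10 days late | 80 | 90 |

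**Step 2: how many are affected.** Expected to miss at least one call: 0.40 × 90 = 36. Total person-days: 90 × 90 = 8,100.

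**Step 3: independent misses, calls otherwise on time.**
- Completion per call: p = 0.6^(1/3) = 0.843, so q = 1 − p = 0.157.
- One-month recall: each month is lost when its own call is missed. Share lost = q = 15.7%, or 14.1 of 90 days per person.
- Recall to last interview: month 1 is lost only if all three calls are missed (q³), month 2 if the last two are missed (q²), and month 3 if the last is missed (q). Share lost = (q³ + q² + q)/3 = (0.004 + 0.025 + 0.157)/3 = 6.2%, or 5.5 days per person.
- Recovered: about 8.5 days per person, or about 769 of 8,100 person-days. This is 9.5% of the total and 61% of the loss.
- Complete 90-day records: 0.60 × 90 = 54 with the one-month recall. With the longer recall a record is complete whenever the last call is made: 0.843 × 90 = about 76.

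**Step 4: other patterns consistent with 60% completion**

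| Pattern among the 36 | Person-days recovered |
|---|---|
| All drop out for good at the first miss | 0 |
| All miss one early call and return | 36 × 30 = 1,080 (13.3%) |
| All miss both early calls and return at day 90 | 36 × 60 = 2,160 (26.7%) |

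**The case against.** **The text is silent rather than restrictive.** A reader might infer that interviewers may ask only about the previous month and that missed days are lost permanently. The documents do not say so. The sentence describes the scheduled case, in which the two windows coincide, and it neither provides for nor forbids a longer recall. The Appendix and the cited follow-back sources are not available, and an operating rule could be there. This stands. It limits the point to what happens if the supplied text is followed literally. It does not remove the need for a stated rule, because interviewers left to improvise may use different windows.

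**The next interview does not recover everything.** A missed day-90 call has no successor, permanent dropouts gain nothing, and a late call can close its own gap. This stands and is built into the counts.

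**The gain may be small.** A reader might also infer that missed calls cluster around relapse, so that the lost month is the informative one. That is plausible, but the documents do not state it. It would also sit badly with the independence calculation: if relapse leads to lasting loss of contact, misses run together and the recovery moves towards nil. The figure of 76 records is therefore one scenario, not a forecast.

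**Longer recall has its own error.** Asking for 60 or 90 days of daily use, in people whom the plan describes as commonly having neurobehavioral deficits, may add recall error. That error could depend on cognition, which is a predictor in E4. This is the strongest objection, and a uniform one-month window is a defensible choice on this ground. But collecting the longer period does not force its use. If the longer-recall days are marked, they can be dropped, which restores the one-month analysis. Days never asked about cannot be added later.

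**Consequence.** Follow-up is a preliminary and exploratory component, and incomplete follow-up is disclosed. This stands and keeps the point minor.

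**Conclusion.** The point holds as a minor, inexpensive improvement to data collection. The protocol states a one-month recall at approximate dates, expects about 36 of 90 participants to miss at least one call, and in the supplied text gives no catch-up provision. Taken literally, each missed day-30 or day-60 call followed by a later contact costs 30 recoverable days, and a call that comes late costs as many days as its delay. This falls short of the stated aim of covering the first 90 days.

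The size is uncertain because the documents give no missingness pattern. Recovery is nil, apart from late-call gaps, if every miss is permanent dropout. It is about 9.5% of person-days if misses are independent, and higher only if most of those who miss early calls return. The stronger reading, that data are permanently lost by design and the next interview would always recover them, is not supported. The primary Stroop analyses are unaffected.

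**What to change.** In the Follow-up paragraph and the interview guide:

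1. Define the follow-back window as running from the last completed interview or, if there is none, from the anchor date (discharge or, for outpatients, the post-training assessment).
2. State the tolerance around days 30, 60 and 90.
3. Record the recall interval for each day, flag days recalled over more than about 30 days, and name a sensitivity analysis for E4 and the secondary aim that excludes them, so that results under the one-month window can be shown beside the main ones.

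Nothing changes for participants whose calls are on time. The cost is a line in the guide, a flag in the database, and longer recall with a longer call (now planned at about 30 minutes) for those who missed an interview. Missed day-90 calls remain unrecovered and still need the planned missing-data methods.
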